2. STUDY OBJECTIVES AND ENDPOINTS

The study objective is to determine if WB001 used adjunctively with TAU can further reduce symptoms of depression for women with mild to moderate PPD beyond that of an educational control application and TAU, at the end of the 8-week treatment period as measured by the change in HAM-D6. The endpoints to support the study objectives are listed in [Table 1](#).

Sponsor Name: Woebot Health

Protocol Number: WB001-001

TABLE 1 STUDY OBJECTIVES, HYPOTHESES, AND ENDPOINTS

Objective	Endpoint

Primary Objective: To evaluate the efficacy of [WB001+TAU] vs [ED001+TAU] on depressive symptoms as measured by a structured clinical interview (with the Hamilton Depression Rating Scale (HAM-D) among women diagnosed with PPD.
 
Secondary Objectives:
 
• To evaluate the efficacy of [WB001+TAU] vs [ED001+TAU] on indices of clinical interest including (1) the Mother-Infant Bonding Scale (MIBS), (2) Edinburgh Postnatal Depression Scale (EPDS), (3) Patient Health Questionnaire (PHQ), and (4) Generalized Anxiety Disorder (GAD)• To evaluate the within-group differences on the HAM-D in the [WB001+TAU] and [ED001+TAU] arms 
Exploratory Objective: Investigate clinically significant between group differences of [WB001+TAU] vs [ED001+TAU] on the Clinical Global Impression (CGI) scales and Patient Global Impression (PGI) scales
	
Difference in HAM-D6 scores between arms at end of treatment (EOT) controlling for baseline (BL) and other covariates
 
• Difference between arms in indices (MIBS; EPDS; PHQ; GAD) at EOT controlling for BL and other covariates• Difference in HAM-D6 scores from BL to EOT within each trial arm 
Difference between arms on Clinical Global Impression of Improvement and Severity (Clinical Global Impression Improvement (CGI-I) the CGI-Severity (CGI-S)) and Patient Global Impression Scales (Patient Global Impression Change (PGI-C) and Patient Global Impression Severity (PGI-S)).

[REDACTED]	[REDACTED]
[REDACTED]	[REDACTED]

AE=adverse event; BL=baseline assessment; Clinical Global Impression - Improvement and Severity (CGI-I; CGI-S).

EOT=end of treatment assessment; EPDS= Edinburgh Postnatal Depression Scale; GAD=Generalized Anxiety Disorder Questionnaire; MIBS=Mother-to-Infant Bonding Scale; Patient Global Impression – Change and Severity (PGI-C; PGI-S); PHQ = Patient Health Questionnaire; SAE=serious adverse event

Sponsor Name: Woebot Health

Protocol Number: WB001-001

3. STUDY DESIGN

3.1 OVERALL STUDY DESIGN

This is a multicenter, double-blind, randomized, controlled trial to evaluate the efficacy and safety of WB001 in adult women with mild to moderate PPD. Eligible participants must have diagnosis of mild to moderate PPD and experience at least mild to moderate symptom severity as evidenced by a score of > 7 and < 13 (i.e., between 8-12, inclusive) on the HAM-D6.

The study will utilize referrals by an obstetrician, pediatrician, or other healthcare professional, or by other digital and site based recruitment methods and direct participants to the closest study site, across up to 25 study centers in the U.S., to schedule and complete a pre-screening/screening appointment. From there, the site staff will schedule their first office visit, during which the site staff with oversight by the investigator, will obtain informed consent and complete the screening and BL assessments. The CIR will be responsible for administration of the HAM-D for the primary endpoint as outlined in [Appendix 3: Schedule of Events](#). To standardize and facilitate administration of the primary endpoint, the Structured Interview Guide for the Hamilton Depression Rating Scale (SIGH-D) will be used (Williams, J.B. 2015).

Participants will then be randomized in a 1:1 manner to either [WB001+TAU] or [ED001+TAU] and will be prompted to install the app on their smartphone. Study site personnel will help the participants with the app installation to streamline enrollment. Participants in both groups will participate in a form of TAU, which is clinician supervised outpatient care including, follow-up visit(s), psychotropic medication, psychotherapy, or some combination thereof. [REDACTED]

[REDACTED] Both treatment arms will be presented as possibly helping to improve PPD and both will be described as the study app so that there is no distinction made to the participants about WB001 or the digital educational control app. Post-randomization, the 8-week treatment period begins when the participant successfully downloads the study app and completes the integrated onboarding process.

Participants will attend a mid-study and EOT (at Week 4 and Week 8) telehealth visit with a CIR, to be assessed based on the HAM-D, a validated standard clinician-rated and participant-rated outcome scales for PPD. Any AE/SAE raised during CIR-administration of HAM-D, will be raised to the PI or qualified designee for final determination on appropriate course of action. At Week 4 and Week 8 the PI or qualified site staff will

Sponsor Name: Woebot Health

[figure not shown]
Protocol Number: WB001-001

administer the C-SSRS, evaluate for concomitant medications/therapy, pregnancy status, and safety throughout the duration of the trial.

At Week 4 and 8, participants will be prompted to complete several online self-report assessments (e.g., EPDS, PHQ-9, MIBS, GAD-7 and PGI) within 3-days prior to or 3-days after the visit date. The same assessment steps in Week 4 will apply to Week 8 (EOT) visits, with the addition that at Week 8 participants will receive instructions about how to uninstall the app and will go through other end-of-study procedures.

Not including the referral period and potential for participants to complete the last self-reported assessments 3 days after the week 8 visit, the duration of study participation is 8 weeks. [Figure 3](#) shows the overall Study Schematic.

Figure 3. Study Schematic

[figure not shown]
[figure not shown]

Sponsor Name: Woebot Health

Protocol Number: WB001-001

3.2 RATIONALE FOR DURATION OF TREATMENT

As discussed, CBT and IPT have robust efficacy for the treatment of depression in adults including PPD. Although there is no exact standard length of treatment (cognitive behavioral therapy, 2011), flagship models of CBT and IPT were delivered over the course of 12-20 sessions. However, briefer interventions, including guided self-help adaptations of the therapies, have demonstrated meta-analytic level efficacy and durability of effect for depression, including those which are six or fewer weekly sessions (Cuijpers, et al., 2019). Typically, CBT guided self-help delivery ranges from 6 to 8 sessions total (Barth, et al., 2013). A 2021 meta-analysis of online CBT guided self-help interventions found no significant differences on depression outcomes between groups that were short (≤ 4 weeks), moderate ($= 4-8$ weeks), and greater (≥ 8 weeks) in length (Ma et al., 2021).

Sponsor Name: Woebot Health

Protocol Number: WB001-001

[REDACTED]

[REDACTED]

[REDACTED]

3.4 SCIENTIFIC RATIONALE FOR STUDY DESIGN

To prevent bias in treatment allocation and assessment of treatment effect, the study is randomized.

The chosen efficacy objectives and endpoints represent standard assessments used in clinical studies of treatments for depression and reflect clinically meaningful outcomes for patients with PPD and the clinicians who treat them.

[REDACTED]

The safety data will also add to the Sponsor's understanding of AEs that might be associated with WB001.

The study is designed with telehealth visits, which are more convenient for study participants , and accommodate the need to comply with recommended social distancing recommendations for reducing transmission of Severe Acute Respiratory Syndrome Coronavirus 2 (SARS-CoV-2).

A participant is considered to have completed the study if she has completed at least BL and Week 4 or Week 8 for primary HAM-D6. The end of the study is defined as the date of the last visit or last procedure of the last participant in the study.

3.5 BLINDING

This is a double-blind study. Participants will not be made aware to which intervention they are assigned and will be randomized to receive the active treatment app (WB001) or the Educational Control (ED001). Thus, participants, clinicians, and the clinical site study team will be blinded to treatment allocation to the extent possible throughout the study period and database lock.

[REDACTED]

[REDACTED]

Sponsor Name: Woebot Health

Protocol Number: WB001-001

A high-contrast, black and white image showing a series of horizontal bars of varying lengths. The bars are mostly black, set against a white background. Some bars have small white segments at their ends. The lengths of the bars decrease from top to bottom. The image is heavily processed, appearing as a binary black and white pattern.

Sponsor Name: Woebot Health

Protocol Number: WB001-001

Term	Percentage
GMOs	75
Organic	85
Natural	70
Artificial	25
Organic	88
Natural	72
Artificial	28
Organic	82
Natural	68
Artificial	22
Organic	80
Natural	65
Artificial	20
Organic	84
Natural	71
Artificial	26
Organic	86
Natural	73
Artificial	27
Organic	87
Natural	74
Artificial	28
Organic	89
Natural	76
Artificial	29
Organic	91
Natural	78
Artificial	30
Organic	93
Natural	80
Artificial	32
Organic	95
Natural	82
Artificial	34
Organic	97
Natural	84
Artificial	36
Organic	98
Natural	85
Artificial	37
Organic	99
Natural	86
Artificial	38
Organic	100
Natural	87
Artificial	39

CON

Sponsor Name: Woebot Health

Protocol Number: WB001-001

TABLE 2 BLINDING PLAN

Role	Event			
	Randomization / Treatment Allocation	Week 4, 8 Assessments	Interim Analysis	Final Analysis
Participants	B	B	B	B
PI and Site staff to administer assessments	B	B	B	B
One Site Coordinator to assist with app registration/download	UB	UB	UB	UB
Site/Central Independent Rater	B	B	B	B
DSMB Statistician will generate the randomization schedule and run analysis queries requested by DSMB members	UB	UB	UB	UB
Independent (non DSMB) statistician and	B	B	B	B

Sponsor Name: Woebot Health

Protocol Number: WB001-001

programmer/data analysts for Interim Analysis and Final Analysis (prespecified in SAP)				
B = Blinded; UB = Unblinded				

3.6 PROCEDURE FOR BREAKING THE BLIND

In the event that a CIR, PI, or blinded site staff member is inadvertently unblinded, the site will be provided with SOPs detailing the appropriate procedure for each of the following scenarios:

1. Unblind a participant and or other study staff in an emergency situation
2. Unblind data for the purpose of notification to the Data Safety Monitoring Board (DSMB)
3. Manage and mitigate accidental unblinding

In the case of an emergency, the investigator has the sole responsibility for determining if unblinding of a participants' intervention assignment is warranted. Accidental unblinding, which may occur during discussions between the participant and trial PI and site staff, would not impact the primary endpoint which will be collected by CIRs. Any potential unblinding at the CIR level may trigger replacement of the rater. All instances of unblinding will be recorded and assessed for comparability between the groups.

4. STUDY POPULATION

Eligible participants who are enrolled in the trial will be assigned a unique participant randomization number for study app functionality assignment at baseline. Only participants who meet all the inclusion criteria and none of the exclusion criteria will be eligible to participate in the study. Prospective approval of protocol deviations to recruitment and enrollment criteria, also known as protocol waivers or exemptions, is not permitted.

4.1 INCLUSION CRITERIA

A participant will be eligible for entry into the study if all the following inclusion criteria are met:

1. Participants must have primary residence in the United States
2. Participant must be willing to comply with all study procedures and restrictions
3. Participants must be able to understand and be willing to provide informed consent
4. Participants must be ≤ 92 days postpartum at the time of screening
5. Participants must be women aged 22-45 years who had onset of a major depressive episode during pregnancy or within 4 weeks following delivery according to DSM-5 diagnostic criteria (Segre et al., 2013)

Sponsor Name: Woebot Health

Protocol Number: WB001-001

- 7. Participants must own or have regular access to a smartphone (Android or iOS smartphone with a recent, supported operating system), and has reliable Wi-Fi access or sufficient data plan to engage with assigned treatment condition for the duration of the study
- 8. Participants must have current mild-moderate depression as measured by the HAM-D6 score > 7 and < 13 at Screening (Bech et al., 2007; Pridmore et al., 2020)
- 9. Participants must confirm having a form of TAU, defined as clinician supervised outpatient care management and includes follow-up visits, medication, psychotherapy, or some combination thereof.
- 10. As part of TAU during the study, any confirmed concomitant medications and psychotherapy are permissible and must be regularly scheduled or stable (i.e., dose and frequency, respectively) for over 4 weeks prior to BL visit

4.2 EXCLUSION CRITERIA:

A participant will not be eligible for study entry if any of the following exclusion criteria are met:

- 1. Gestation less than 28 weeks
- 2. HAM-D6 score, ≤ 7 or ≥ 13 (severe depression) at Screening
- 3. Currently pregnant or plans to become pregnant within the next 8 weeks
- 4. History of drug and/or alcohol use disorder within the past 12 months as measured by the SCID-5-CT
- 5. Lifetime history of suicide attempt or ideation with a plan and intent to harm oneself during the current episode of PPD
- 6. Current or lifetime psychosis, including history of post- or peri-partum psychosis as measured by the SCID-5-CT (Williams JB, 2015)
- 7. Current or lifetime history of schizophrenia, schizoaffective disorder, bipolar disorder, and/or homicidal or infanticidal ideation as measured by the SCID-5-CT
- 8. History of antidepressant treatment with ketamine/esketamine, electroconvulsive therapy, vagal nerve stimulation, or a deep brain stimulation device
- 9. History of antidepressant treatment with ketamine/esketamine, electroconvulsive therapy, vagal nerve stimulation, or a deep brain stimulation device
- 10. Fetal demise within the past 18 months
- 11. Previous Woebot use

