1.3 INVESTIGATIONAL DEVICE

Sponsor Name: Woebot Health

[figure not shown]
Protocol Number: WB001-001

WB001 is a smartphone application designed for an 8-week treatment period, as an adjunct to TAU for women aged 22-45 years with mild to moderate postpartum depression. Specifically, women must have given birth in the previous 92 days and have no active or recent history with substance(s) abuse, not be currently psychotic, have no lifetime occurrence of psychosis, schizophrenia or bipolar disorder, or a history of suicide attempt or suicidal ideation or a plan or intent to harm oneself during the current episode of postpartum depression, or history of homicidal or infanticidal ideation via self-report. WB001 is intended as a prescription-only adjunctive treatment under the supervision of a clinician.

WB001 was developed based on evidence for mobile mental health applications, and factors associated with positive outcomes in the literature proposed by Bakker and colleagues (2016), including the following:

- Built on a CBT framework
- Incorporates automated tailoring
- Provides mental health information
- [REDACTED]
- Addresses both anxiety and depressed mood
- Simple and intuitive interface and interactions
- Real-time patient engagement and check-in reminders

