However, potential risks include the opportunity cost of seeking alternative treatment, device software failure, leading to delayed access, information security breaches, and potentially brief emotional stress that may result from attending key assessment visits, completing survey questions that cover sensitive topics, and discontinued access to the assigned study intervention at the end of study (Week 8).

Several aspects of the study design will mitigate these potential risks of participating in the study:

- [REDACTED]
- adjunct.
- The eligibility criteria will exclude patients with severe psychiatric diagnoses (e.g., psychosis, history of attempted suicide or current suicidal ideation, substance use disorder).
- Concomitant medications and psychotherapy are allowed during the study period per standard of care as prescribed and administered by trained professionals, as long as the medication doses and frequency of psychotherapy are stable for at least 4 weeks before the Baseline visit. The study will capture any changes (e.g., starting or stopping a medication or any change in medication dose or frequency, as well as changes in frequency of psychotherapy).
- [REDACTED]

Sponsor Name: Woebot Health

Protocol Number: WB001-001

- Survey Questionnaires have been thoughtfully selected to minimize the risk of emotional upset due to the topics covered.
- Woebot performing appropriate software verification and validation testing to demonstrate that the device's behavioral therapy has been correctly implemented so that the participant can access it when needed.
- All study data will be gathered on a secure Health Insurance Portability and Accountability Act (HIPAA)-compliant web platform and will be encrypted to minimize the risk of a data breach.
- Participants will be informed that they may leave the study at any time and can receive appropriate referrals for alternative treatment.
- Participants will have contact with the investigator and/or designated clinical rater at each study assessment time point, who will administer validated psychometric assessments to monitor for worsening symptoms and/or the development of suicidal ideation.
- Study withdrawal criteria are designed so that participants who experience worsening of symptoms can withdraw from the study to receive additional treatment, per PI recommendation.

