SUICIDAL IDEATION AND BEHAVIOR RISK MONITORING

[figure not shown]
Sponsor Name: Woebot Health

Protocol Number: WB001-001

The study design includes assessment of suicidal ideation as described. All participants will meet with the investigator or qualified site staff at Baseline, Week 4, and Week 8 during a telehealth visit, and will be administered psychometric tests (i.e., C-SSRS and HAM-D item #3) to assess suicidal ideation.

C-SSRS

The clinician-administered C-SSRS is a measure used to identify and assess individuals at risk for suicide (The Columbia Lighthouse Project/Center for Suicide Risk Assessment, 2019). The C-SSRS measures four constructs: the severity of ideation, the intensity of ideation, behavior, and lethality. The C-SSRS is made up of ten categories, with binary responses (Yes or No) to indicate presence or absence of the behavior, and the outcome is a numerical score obtained from these categories. The C-SSRS will be administered by the investigator or qualified site staff during telehealth visits at baseline, Week 4, and Week 8 to monitor for potential onset of suicidal ideation. If a score on the C-SSRS raises a safety concern, i.e., 'yes' on questions 4 or 5, or answer 'yes' to "actual attempt" question in "Suicidal Behavior" section the site-based rater will immediately contact the PI/sub-investigator to ensure that the investigator urgently conducts an assessment of this participant to determine the appropriate actions to take and disposition of the participant. Similarly, if a safety concern is raised due to a score submitted through a CIR administered structured clinical interview (a score of ≥ 2 on the HAM-D17 item #3) or self-report ePROs (a score of ≥ 2 on item #9 of PHQ-9 and/or score of > 2 on item #10 of EPDS), an electronic system at the sites will notify the investigator to review each incident and follow up with the participant within 24 hours to determine if any action is required. If so, the investigator will be responsible for administering a formal assessment using the C-SSRS, if deemed necessary.

Sponsor Name: Woebot Health

Protocol Number: WB001-001

[REDACTED]

[REDACTED]

[REDACTED]

[REDACTED]

[REDACTED]

[REDACTED]

PREGNANCY AND BREASTFEEDING

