7. DATA AND SAFETY MONITORING

Data monitoring will be conducted by the research coordinator and site staff (research team) and overseen by project PIs.

During data collection and monitoring, study coordinators will follow an internal safety protocol and alert a study PI of any clinical concerns. A clinical concern is defined here as any negative experience or symptom that occurs during baseline or post randomization sessions that are raised via email/text/phone correspondence directly by the patient, or in key assessment visits to the CIR, whether it is associated with participation in the study.

The PIs in consultation with study site staff will be responsible for monitoring participant safety during the study and will review relevant data/information to determine whether it is appropriate for the participant to continue study participation and whether further action to ensure the safety and wellbeing of the participant is warranted.

Given this study will be conducted among women with PPD, there are clinical concerns that may be anticipated in the target patient population due to the natural course of disease. Anticipated clinical concerns may include suicidal ideation, clinically significant deterioration in depressive symptoms, self-injurious behavior, suicide attempts, and completed suicide. These events will be recorded and will be elevated to AE or SAE status if deemed appropriate by the investigator, and promptly reported to the Sponsor. As part of a Safety Monitoring process, all AEs/SAEs will require DSMB review, and the Sponsor can query any PI-determined AEs/SAEs.

TABLE 3 CLINICAL CONCERN CATEGORIZATIONS

Clinical Concern	Definition
0 - Not a clinical concern:	Qualified research personnel determined that triggering event was not a clinical concern

Sponsor Name: Woebot Health

Protocol Number: WB001-001

1- Mild clinical concern:	Qualified research personnel determined that triggering event doesn't require investigator input and will continue to monitor participant's responses
2- Moderate clinical concern:	Qualified research personnel determined that triggering event requires investigator input. PI/Clinician determined that the research team should continue to monitor participant's responses but that no follow-up was needed.

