3- Elevated clinical concern:	Qualified research personnel determined that triggering event requires clinician input. PI/Clinician determined follow-up was indicated and confirmed participant safety (participant did not endorse intent to self-harm) via email or phone communication with participant or their provider.
4- Significant clinical concern:	Qualified research personnel determined that triggering event requires clinician input. PI/Clinician determined that follow-up was indicated and after follow-up with participant, parent/guardian, or provider determined that participant should be withdrawn from study (e.g., due to suicide attempt, self-harm or self-harm attempt, suicidal ideation with intent, reported hospitalization for self-harm or suicide attempt while enrolled in study).

All clinical concerns documented as level 4 of concern will be reported to the DSMB for review and oversight within 5 working days to ensure patient safety and efficient monitoring. In addition, appropriate reporting will be done to notify the Sponsor and IRB per details in Section [10.2](#) Institutional Review Board.

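### Exclusion criterion 5 requires both a plan and intent, so suicidal intent without a plan is not excluded, although three other parts of the protocol are stricter

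*Combined protocol and SAP*

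**What the plan says.** **Entry.** Section 4.2, criterion 5, and the Synopsis list of key exclusions use the same words: "Lifetime history of suicide attempt or ideation with a plan and intent to harm oneself during the current episode of PPD". Section 4 makes the numbered list decisive: "Only participants who meet all the inclusion criteria and none of the exclusion criteria will be eligible to participate in the study". It also bars waivers.

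**Device population.** Section 1.3 describes the intended users as women without "a history of suicide attempt or suicidal ideation or a plan or intent to harm oneself" in the current episode.

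**Benefit/risk.** The Benefit/Risk Assessment offers the eligibility criteria as a mitigation and says they keep out patients with, among other things, "history of attempted suicide or current suicidal ideation".

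**Withdrawal.** In Section 7, Table 3, level 3 covers a participant for whom follow-up "confirmed participant safety (participant did not endorse intent to self-harm"). Level 4 is reached when follow-up leads the PI or clinician to decide that the "participant should be withdrawn from study (e.g., due to suicide attempt, self-harm or self-harm attempt, suicidal ideation with intent". Section 7 defines the concerns graded in this table as "any negative experience or symptom that occurs during baseline or post randomization sessions".

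**Baseline handling.** The C-SSRS is scheduled at the screening/baseline visit (Appendix 3). Under Section 5.3, a positive answer on question 4 or 5, or on actual attempt, makes the rater call the investigator at once. The investigator then assesses the woman urgently to "determine the appropriate actions to take and disposition of the participant".

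**The concern.** The rule that decides who enters is looser on suicidal intent than the text that justifies the risk, the text that describes the device's users, and the table that says when a participant should leave. A woman with intent and no plan meets none of the readable exclusions, yet her state is one that Table 3 names as a reason for withdrawal.

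What is at stake is participant safety and uniform conduct. The benefit/risk argument describes a screen that criterion 5 does not deliver. An investigator who sees such a woman must decide without a written criterion, and investigators at up to 25 centers may decide differently. One arm is an educational control, so the question matters for both allocations.

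**Working it through.** No statistical calculation applies. The check sets the rules side by side and then looks for anything else that would close the gap.

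**Step 1: the combinations.** Among women with ideation in the current episode, plan (no/yes) by intent (no/yes) gives 2 × 2 = 4 combinations.

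| Ideation with | Criterion 5 | Table 3, level 4 example | Section 1.3 | Benefit/Risk, if ideation is current |
|---|---|---|---|---|
| neither | not excluded | not listed | outside | excluded |
| plan only | not excluded | not listed | outside | excluded |
| intent only | not excluded | listed | outside | excluded |
| both | excluded | listed | outside | excluded |
| **Combinations covered** | **1** | **2** | **4** | **4** |

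Criterion 5 against Table 3 differs by 2 − 1 = 1 combination: intent without a plan. Against Section 1.3, and against the Benefit/Risk Assessment for current ideation, it differs by 4 − 1 = 3. These are counts of wording, not of women; the combinations are not equally common or equally grave.

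**Step 2: could another readable criterion exclude her?**
- Exclusion 7 concerns homicidal or infanticidal ideation only.
- The HAM-D6 band of 8 to 12 does not test for suicidality. Section 5.2 builds the HAM-D6 from items 1, 2, 7, 8, 10 and 13, whereas Section 5.3 uses HAM-D17 item 3 for suicide monitoring.
- No C-SSRS result is written as an exclusion.
- Inclusion criterion 6 cannot be read.

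**Step 3: could she be stopped before randomization anyway?** Appendix 3 places randomization after the baseline assessments and after all criteria are met. The C-SSRS is one of those assessments, and its escalation is immediate. Table 3 also reaches baseline sessions. An investigator would therefore probably see her before allocation. Two qualifications apply. The protocol does not print the C-SSRS questions, so the document alone does not show exactly which combinations set off the flag. The alerts from HAM-D17 item 3, PHQ-9 item 9 and EPDS item 10 allow 24 hours for follow-up, which could end after a same-day randomization.

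**Result.** A route to stop her exists, but it is a judgement after a flag and not a stated ground for exclusion.

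**The case against.** The best defense is that the gap closes at the same visit. If Table 3 applies at baseline, so does its remedy: the clinician follows up and can decide that she should not continue. The baseline C-SSRS sends a flagged woman to the investigator before randomization. The Synopsis leaves the eligibility decision to the PI or sub-investigator, and Section 4.6 requires treatment to stop if continuing would harm her. Entry and withdrawal rules also need not match word for word. Level 4 is a list of examples applied after follow-up, and its closing reference to being enrolled may qualify the whole list or only hospitalization (Section 8.2 counts a woman as enrolled once she has signed consent).

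Most of this stands, and it limits the consequence. A reader might infer that she would be randomized and recognized only at a later contact. The documents do not support that, because the C-SSRS and Table 3 both operate at baseline. A reader might also infer that the bar on waivers obliges sites to admit her. It does not: it stops sites from admitting women who fail a criterion and says nothing against declining someone on safety grounds.

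Redaction is a further fair point. Besides inclusion criterion 6, the unplanned-visit triggers, text after the C-SSRS section, the escalation scenarios in Appendix 3 and some mitigation bullets are blacked out. A rule there could bear on this case.

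The mismatch itself survives. The Benefit/Risk Assessment attributes the exclusion of current ideation to the eligibility criteria, and the readable criteria do not contain it.

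**Conclusion.** The inconsistency is real: criterion 5 is looser on intent without a plan than Section 1.3, the Benefit/Risk Assessment and Table 3, and no readable criterion covers that state. Its size is one combination of four against Table 3. The documents give no frequency for it, so no number of affected women can be stated.

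The practical risk is moderated by the baseline C-SSRS and investigator judgement. What remains is that protection depends on discretion where a criterion could settle it. The conclusion assumes that the redacted text does not already contain an equivalent rule, so confidence is moderate.

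This is a change to consider on safety and consistency grounds. It should not be read as a threat to the primary analysis: Section 4.6 asks withdrawn women to keep attending visits unless they withdraw consent for follow-up, and it allows replacement.

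**What to change.** In Section 4.2 and the Synopsis, reword criterion 5 along these lines: *lifetime suicide attempt, or suicidal ideation with intent to harm herself, with or without a plan, in the current PPD episode, as judged from the baseline C-SSRS before randomization*. This puts the entry threshold where Table 3 separates level 3 from level 4. The smallest edit is to replace *and* with *or* between plan and intent, which closes the same gap and also excludes a plan without intent.

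Do not narrow Section 1.3 or the Benefit/Risk Assessment to fit. That would loosen stated safety text. If the sponsor means the threshold given there (any current ideation), criterion 5 should be tightened further to match.

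The cost is a protocol amendment with IRB approval and a small, unquantified number of additional screen failures. No visit or instrument is added, because the C-SSRS is already scheduled at baseline ahead of randomization.
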